3.3.2 Exclusion Criteria

1) Target Disease Exceptions

- a) Known or suspected, acquired or bleeding or coagulation disorder in the subject or a first degree relative
- b) Known coagulopathy
- c) Active bleeding or at high risk for bleeding.

2) Medical History and Concurrent Diseases

- a) Brain, spinal, ophthalmologic, or major surgery or trauma within the past 90 days
- b) Active hepatobiliary disease
- c) Alcohol and/or substance abuse within the past year
- d) Any condition, in the opinion of the Investigator, for which surgery or administration of an anticoagulant is contraindicated.

3) Physical and Laboratory Test Findings

- a) Two consecutive blood pressure readings within 15-30 minutes with supine SBP > 180 mm Hg or supine DBP > 105 mm Hg
- b) Hemoglobin < 9 g/dL
- c) Platelet count < 100,000/mm³
- d) Creatinine clearance < 30 mL/min as estimated by the method of Cockcroft and Gault
- e) Active hepatobiliary disease, based on an ALT or AST > 2 x ULN or a Total Bilirubin ≥ 1.5 x ULN (unless an alternative causative factor [eg, Gilbert's syndrome] is identified).

4) Sex and Reproductive Status

- a) WOCBP who are unwilling or unable to use an acceptable method to avoid pregnancy for the entire treatment period of the study

- b) Women who are pregnant or breastfeeding
- c) Women with a positive pregnancy test on enrollment or prior to investigational product administration.

5) Other Exclusion Criteria

- a) Prisoners or subjects who are involuntarily incarcerated
- b) Subjects who are compulsorily detained for treatment of either a psychiatric or physical (eg, infectious disease) illness
- c) Administration of any investigational drug currently or within 30 days prior to enrollment into this study.

6) Prohibited Treatments and/or Therapies

- a) Any antiplatelet agents (including clopidogrel) other than aspirin
- b) Vitamin K antagonist or other novel oral anticoagulant (such as rivaroxaban or dabigatran) during the treatment period
- c) Ongoing unfractionated heparin or low molecular weight heparin use
- d) Use of thrombolytics within past 7 days
- e) Use of Fondaparinux

Eligibility criteria for this study have been carefully considered to ensure the safety of the study subjects and to ensure that the results of the study can be used. It is imperative that subjects fully meet all eligibility criteria.

3.3.3 *Women of Childbearing Potential*

Women of childbearing potential include any female who has experienced menarche and who has not undergone successful surgical sterilization (hysterectomy, bilateral tubal ligation, or bilateral oophorectomy) or is not postmenopausal. Post menopause is defined as:

- Amenorrhea ≥ 12 consecutive months without another cause and a documented serum follicle stimulating hormone (FSH) level > 35 mIU/mL or
 - Women with irregular menstrual periods and a documented serum follicle stimulating hormone (FSH) level > 35 mIU/mL or
- NOTE: FSH level testing is not required for women ≥ 62 years old with amenorrhea of ≥ 1 year
- Women on hormone replacement therapy (HRT).

Women who are using oral contraceptives, other hormonal contraceptives (vaginal products, skin patches, or implanted or injectable products), or mechanical products such as an intrauterine device or barrier methods (diaphragm, condoms, spermicides) to prevent pregnancy, or are practicing abstinence or where their partner is sterile (eg, vasectomy) should be considered to be of childbearing potential.

3.4 Concomitant Treatments

Medications required for the treatment of underlying medical conditions are allowed, with the exception of those listed below.

3.4.1 Prohibited and/or Restricted Treatments

Prohibited Therapies

Prohibited medications are listed in the Exclusion Criteria (see [Section 3.3.2](#) item 6a to 6e).

Use of pneumatic compression devices and tourniquets must be discontinued at the completion of skin wound closure and are not permitted throughout the treatment period.

Anti-thrombotic prophylaxis may be continued during the follow-up period per the Investigator's discretion and standard of care.

Restricted Therapies During the Treatment Period

Subjects are allowed to use the following therapies during the study at the investigator's discretion:

- Oral cox-2 selective (eg, celecoxib [Celebrex®]) and short-acting NSAIDs for joint pain are permitted although not encouraged (acetaminophen/paracetamol or opioids are the preferred methods for systemic pain management)
- Parenteral ketorolac or parecoxib is permitted although not encouraged (acetaminophen/paracetamol or opioids are the preferred methods for systemic pain management)
- Aspirin > 165 mg/day is prohibited
- Herbal medications are permitted, provided the subject has permission from the Investigator
- Metformin should be temporarily discontinued at the time of, or prior to, procedures in which intravascular iodinated contrast material is used and then withheld for at least 48 hours subsequent to the procedure (eg, venograms).
- Epidurals should be removed at least 5 hours prior to administration of the first dose of apixaban.

All concomitant medication use must be noted on the appropriate e-CRFs.

3.4.2 Other Restrictions and Precautions

The following precautions and restrictions must be followed to preserve study integrity and subject safety:

- Subject should comply with prescribed dosing schedule
- Subjects should be cautioned that any new prescriptions, or over-the-counter medications, including herbal medications, should be discussed thoroughly with the Investigator prior to initiation.

Study medication must be discontinued for subjects experiencing a severe adverse event, (eg, myocardial infarction) which may require the use of open-label anticoagulants (eg, LMWH), antiplatelet agents, thrombin inhibitors (eg, hirudin), glycoprotein IIb/IIIa antagonists or other antithrombotic agents, either with or without interventions (eg, percutaneous coronary intervention). The treating physician should be made aware that when study medication (apixaban) is administered at the protocol-specified doses, routine coagulation tests such as Prothrombin Time (PT) and Activated Partial Thromboplastin Time (aPTT) are relatively insensitive measures of activity and, therefore, unsuitable for monitoring. If treatment of a severe adverse event is indicated, the treating physician may consider using the agent(s) listed above at the lowest recommended therapeutic dose for the first 12 hours following discontinuation of study medication.

Discontinuation of Subjects from Treatment: Subjects MUST discontinue investigational product (and noninvestigational product at the discretion of the investigator) for any of the following reasons:

- Withdrawal of informed consent (subject's decision to withdraw for any reason)
- Any clinical adverse event (AE), laboratory abnormality or intercurrent illness which, in the opinion of the investigator, indicates that continued participation in the study is not in the best interest of the subject
- Pregnancy
- Termination of the study by Bristol-Myers Squibb (BMS)
- Loss of ability to freely provide consent through imprisonment or involuntary incarceration for treatment of either a psychiatric or physical (eg, infectious disease) illness
- Signs and/or symptoms suggestive of DVT in the operated and/or nonoperated leg which are confirmed by ultrasound and/or venography
- Signs and/or symptoms suggestive of PE which are confirmed by diagnostic assessment, eg, V/Q scan, pulmonary angiogram, CT scan (including spiral), and as indicated, additional confirmatory tests
- Subject has clinical jaundice at any time
- Subject has specific elevated liver function test (LFTs) results
- Subject has a severe adverse event that may require the use of anticoagulants, antiplatelet agents, thrombin inhibitors, glycoprotein IIB/IIIa antagonists or other thrombotic agents
- Subject has an increased risk of bleeding complications eg persistent bleeding after surgery or difficult (more than 2 failed attempts) or traumatic (bloody spinal fluid) lumbar puncture.

All subjects who discontinue should comply with protocol specified follow-up procedures as outlined in [Section 5](#). The only exception to this requirement is when a subject withdraws consent for all study procedures or loses the ability to consent freely (ie, is imprisoned or involuntarily incarcerated for the treatment of either a psychiatric or physical illness).

If a subject was withdrawn before completing the study, the reason for withdrawal must be entered on the appropriate case report form (CRF) page.

All subjects who discontinue study medication prematurely and have received at least one dose of post-surgical oral study medication should be encouraged to return for an in person visit on Day 7, Day 12 (TKR) or Day 35 (THR) and follow up visit at Day 42 (TKR) or Day 65 (THR). Alternatively those visits would be performed by phone.

Subjects who require a revision of their hip or knee replacement during the study's treatment period should have their apixaban stopped at least 48 hours before their revision surgery.

Patients who withdraw consent for treatment with study drug should still receive follow-up for adverse events and outcomes unless they withdraw consent for follow-up as well.

If a subject is lost to follow-up, every effort should be made to contact the subject and perform these procedures. At minimum the vital status should be collected.

4 TREATMENTS

All protocol-specified investigational and non-investigational products are considered study drug. The following table ([Table 4.1-1](#)) describes the study drug used.

4.1 Study Treatments

[REDACTED]	[REDACTED]						
[REDACTED]	[REDACTED]	[REDACTED]	[REDACTED]	[REDACTED]	[REDACTED]	[REDACTED]	[REDACTED]
[REDACTED]	[REDACTED]	[REDACTED]	[REDACTED]	[REDACTED]	[REDACTED]	[REDACTED]	[REDACTED]
				[REDACTED]			

4.1.1 Investigational Product

An investigational product, also known as investigational medicinal product in some regions, is defined as follows:

A pharmaceutical form of an active substance being tested or used as a reference in a clinical study, including products already with a marketing authorization but used or assembled (formulated or packaged) in a way different from the authorized form, or used for an unauthorized indication, or when used to gain further information about the authorized form. Apixaban 2.5 mg will be the only investigational product in this study.

The investigational product should be stored in a secure area according to local regulations. It is the responsibility of the investigator to ensure that investigational product is only dispensed to study subjects. The investigational product must be dispensed only from official study sites by authorized personnel according to local regulations.

In this protocol, investigational product(s) is apixaban.

4.1.2 Noninvestigational Product

Other medications used as support or escape medication for preventative, diagnostic, or therapeutic reasons, as components of the standard of care for a given diagnosis, may be considered as non-investigational products.

In this protocol, noninvestigational product(s) is/are: Not applicable for this study.

4.1.3 Handling and Dispensing

The product storage manager should ensure that the study drug is stored in accordance with the environmental conditions (temperature, light, and humidity) as determined by the sponsor. If concerns regarding the quality or appearance of the study drug arise, do not dispense the study drug and contact the sponsor immediately.

Storage facilities for controlled substances must be securely locked and substantially constructed, with restricted access to prevent theft or diversion, as applicable by local regulations.

Apixaban tablets should be stored at below 30°C.

4.2 Method of Assigning Subject Identification

At screening, each subject will be assigned a unique sequential number by the Interactive Voice Response System (IVRS). The IVRS will be available 24 hours per day, seven days a week. The subject number will consist of a unique 5-digit number which is assigned sequentially within a study (starting with 00001) by the IVRS. This number will be used for identification throughout the study and will not be used for any other subject.

After meeting inclusion/exclusion criteria, subjects eligible for the treatment will be assigned prior to surgery to apixaban 2.5 mg by the IVRS.

4.3 Selection and Timing of Dose for Each Subject

Study medication for this study is defined as apixaban 2.5 mg tablets. Subjects will receive apixaban tablets.

- The first oral dose will be given 12 - 24 hours after completing skin wound closure, typically in the morning of Day 2, followed by BID dosing for 12 ± 2 days in subjects undergoing TKR or 35 ± 2 days in subjects undergoing THR.
- Study subjects will take one tablet in the morning and one tablet in the evening.

4.4 Blinding/Unblinding

Not applicable.

4.5 Treatment Compliance

Prior to leaving the hospital, subjects or their caregivers will be instructed on timing and proper methods of study medication administration

4.6 Destruction and Return of Study Drug

4.6.1 Destruction of Study Drug

If study drugs (those supplied by the sponsor or sourced by the investigator) are to be destroyed on site, it is the investigator's responsibility to ensure that arrangements have been made for the disposal, procedures for proper disposal have been established according to applicable regulations, guidelines and institutional procedures, and appropriate records of the disposal have been documented. The unused study drugs can only be destroyed after being inspected and reconciled by the responsible BMS Study Monitor.

4.6.2 Return of Study Drug

Study drug will not be returned. All unused and/or partially used study drug may be destroyed on site providing the site has an applicable standard operating procedure on file.

If the site is not able to destroy the study medication, the Study Monitor should be contacted to organize the study drug return.

5 STUDY ASSESSMENTS AND PROCEDURES

5.1 Flow Chart/Time and Events Schedule

Table 5.1-1: Screening Procedural Outline for TKR Subjects (CV185158)

Procedure - TKR Subjects	Screening Visit	Enrollment	Treatment Period					Follow up Period	Notes
			Surgery	Day 2	Hospital Discharge	Day 7	Day 12		
Days	Pre-Surgery 1-14	Pre-Surgery -4 days to +24 hours	Surgery Day 1	Day 2	Hospital Discharge	Day 7 ± 2 days	Day 12 ± 2 days	Day 42 ± 2 days	
Informed Consent	X								
Inclusion/Exclusion Criteria	X								
Medical History	X								
Weight & Age & Gender	X								
Vital Signs (SBP/DBP & HR)	X								
Contact IVRS	X	X							At screening, after obtaining signed informed consent form, contact IVRS to obtain subject number; At enrollment, contact IVRS for assignment to apixaban 2.5 mg
Dispense Study Medication			X						
Discharge Instructions					X				
Review Medication Compliance					X	X	X		
AE/SAE Assessment		X	X	X	X	X	X	X	Lab: for SAE's related to liver failure/jaundice/hepatitis: local lab hepatitis panels and full LFT's (AST, ALT, T.Biliruin, D. bilirubin, GGT, AP, PT/aPTT/INR) must be performed; for bleeding related

Table 5.1-1: Screening Procedural Outline for TKR Subjects (CV185158)

Procedure - TKR Subjects	Screening Visit	Enrollment	Treatment Period					Follow up Period	Notes
			Surgery Day 1	Day 2	Hospital Discharge	Day 7 ± 2 days	Day 12 ± 2 days		
Days	Pre-Surgery 1-14	Pre-Surgery -4 days to +24 hours	Surgery Day 1	Day 2	Hospital Discharge	Day 7 ± 2 days	Day 12 ± 2 days	Day 42 ± 2 days	SAE's, analysis of CDC, PT/aPTT/INR must be performed by the local lab.
Symptomatic VTE Assessment		X	X	X	X	X	X	X	
Local Lab: Serum Creatinine LFT's (AST, ALT, TBIL) & CBC	X	X							
Local Lab: Hb	X	X			X				
Dosing Diaries to be collected						X	X		
Pregnancy Test	X	X			X		X		

Table 5.1-2: Screening Procedural Outline for THR Subjects (CV185158)

Procedure - THR Subjects	Screening Visit	Enrol-ment	Treatment Period					Follow up Period	Notes
Days	Pre-Surgery 1-14	Pre-Surgery -4 days to +24 hours after surgery	Surgery Day 1	Day 2	Hospital Discharge	Day 7 ± 2 days	Day 35 ± 2 days	Day 65 ± 2 days	
Informed Consent	X								
Inclusion/Exclusion Criteria	X								
Medical History	X								
Weight & Age & Gender	X								
Vital Signs (SBP/DBP & HR)	X								
Contact IVRS	X	X							At screening, after obtaining signed informed consent form, contact IVRS to obtain subject number; At enrollment, contact IVRS for assignment to apixaban 2.5 mg
Dispense Study Medication			X						
Discharge Instructions					X				
Review Medication Compliance					X	X	X		
AE/SAE Assessment		X	X	X	X	X	X	X	Lab: for SAE's related to liver failure/jaundice/hepatitis: local lab hepatitis panels and full LFT's (AST, ALT, T.Biliruin, D. bilirubin, GGT, AP, PT/aPTT/INR) must be performed; for bleeding

Table 5.1-2: Screening Procedural Outline for THR Subjects (CV185158)

Procedure - THR Subjects	Screening Visit	Enrol- ment	Treatment Period					Follow up Period	Notes
			Surgery Day 1	Day 2	Hospital Discharge	Day 7 ± 2 days	Day 35 ± 2 days		
Days	Pre- Surgery 1-14	Pre- Surgery -4 days to +24 hours after surgery							
Symptomatic VTE Assessment		X	X	X	X	X	X	X	related SAE's, analysis of CDC, PT/aPTT/INR must be performed by the local lab.
Local Lab: Serum Creatinine LFT's (AST, ALT, TBILI) & CBC	X	X							
Local Lab: Hb	X	X			X				
Dosing Diaries to be collected						X	X		
Pregnancy Test	X	X			X		X	WOCBP only	

5.2 Study Materials

BMS will supply the sites with the following materials:

- Daily dosing diaries to be used to record study medication taken
- Subject discharge instruction cards
- Electronic case report forms
- Sample source documentation worksheets
- Patient Emergency card.

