3.1.3 Treatment Period

The day of surgery is Day 1.

The first dose of apixaban will be administered 12 - 24 hours after completing skin wound closure, typically in the morning of Day 2 and then BID for 35 ± 2 days for the subjects undergoing total hip replacement or 12 ± 2 days for the subjects undergoing total knee replacement.

While hospitalized, subjects will be evaluated on Day 1, Day 2 and discharge day for suspected symptomatic VTE, bleeding events or any AEs or SAEs.

At any subsequent treatment visits (Day 7 ± 2 and Day 12 ± 2 for TKR subjects or Day 7 ± 2 and Day 35 ± 2 for THR subjects), subjects will be instructed to report to the investigator all AEs, including signs and/or symptoms suggestive of VTE and any bleeding events they experienced since their last visit. Subjects with signs and/or symptoms of VTE at any time should return to the hospital/clinic and undergo appropriate diagnostic evaluation.

If study medication is discontinued for a suspected DVT and or PE, alternative antithrombotic prophylaxis may be initiated per the Investigator's discretion and standard of care. Every effort

must be made to confirm a suspected DVT and/or PE diagnosis before discontinuing study medication and initiating treatment per the Investigator's standard of care.

Samples for laboratory assessment of hematology will be obtained on the day of discharge.

Urine pregnancy test will be performed on Day 12 for TKR subjects and on Day 35 for THR subjects.

Dosing Diaries should be collected at Day 7 & Day 12 for TKR subjects and at Day 7 & Day 35 for THR subjects.

Subjects should be encouraged to return for an in person visit on Day 7 and Day 12 for TKR and Day 7 and Day 35 for THR. Alternatively those visits would be performed by phone.

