5.3 Safety Assessments

Bleeding is the primary safety outcome measure. Bleeding AEs/SAE/s will be assessed by the investigator at every post-surgery visit. At discharge from the hospital, impress upon the subject and/or caregiver the importance of contacting the Investigator immediately if subject experiences signs of clinically over bleeding during the treatment period or the follow-up period. These bleeding AEs/SAEs will be evaluated by the clinical events adjudication committee.

Acute clinically overt bleeding is defined as new onset, visible bleeding or signs or symptoms suggestive of bleeding with confirmatory imaging techniques which can detect the presence of blood (eg, US, CT, MRI).

All acute clinically overt bleeding events will be adjudicated by the ICAC as a major bleeding event, a clinically relevant nonmajor bleeding event or neither.

The definition of major bleeding described below is adapted from the International Society on Thrombosis and Hemostasis (ISTH) definition.

Major Bleeding Event is defined as a bleeding event that is:

- Acute clinically overt bleeding accompanied by one or more of the following:
 - A decrease in hemoglobin (Hb) of 2 g/dL or more over a 24-hour period
 - A transfusion of 2 or more units of packed red blood cells
 - Bleeding that occurs in at least one of the following critical sites:
 - Intracranial
 - Intra-spinal
 - Intraocular (within the corpus of the eye; thus, a conjunctival bleed is not an intraocular bleed)
 - Pericardial
 - An operated joint and requires re-operation or intervention
 - Intramuscular with compartment syndrome
 - Retroperitoneal.
- Bleeding that is fatal.

Clinically Relevant Nonmajor Bleeding event is defined as a bleeding event that is:

- Acute clinically overt bleeding
- Does not satisfy additional criteria required for the bleeding event to be defined as a major bleeding event and meets at least one of the following criteria.
- Epistaxis (nose bleed):
 - Subject seeks medical attention from a physician
 - Subject visits an emergency room
 - Bleeding requires an intervention, eg, nasal pack
 - Single bleeding episode persists for 5 minutes or more.
- Gastrointestinal Bleed:
 - Vomit containing frank blood or coffee ground material which tests positive for blood
 - Endoscopically confirmed bleeding
 - Frank blood per rectum or melanic stools.
- Hematuria:
 - Overt, spontaneous bleeding
 - Bleeding (bloody urine) persists for 24 hours or more after instrumentation.

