6 ADVERSE EVENTS

An *Adverse Event (AE)* is defined as any new untoward medical occurrence or worsening of a pre-existing medical condition in a patient or clinical investigation subject administered an investigational (medicinal) product and that does not necessarily have a causal relationship with this treatment. An AE can therefore be any unfavorable and unintended sign (including an abnormal laboratory finding, for example), symptom, or disease temporally associated with the use of investigational product, whether or not considered related to the investigational product.

Adverse events can be spontaneously reported or elicited during open-ended questioning, examination, or evaluation of a subject. (In order to prevent reporting bias, subjects should not be questioned regarding the specific occurrence of one or more AEs.)

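### Hip subjects have no scheduled contact between Day 7 and Day 35, and the daily diary is described as a tablet record only, so non-major bleeds that qualify under Protocol 5.3 without medical care depend on calls the subject chooses to make or on four weeks' recall.

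*Protocol*

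**What the plan says.** Protocol 3.1.3 and Tables 5.1-1 and 5.1-2 set the treatment-period visits after Day 2 and discharge. For hips they are "Day 7 ± 2 and Day 35 ± 2 for THR subjects"; for knees they are Day 7 ± 2 and Day 12 ± 2. Visits should be in person, but "Alternatively those visits would be performed by phone".

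Bleeding can be captured in three ways:

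- **At visits.** Subjects are to report "any bleeding events they experienced since their last visit" (3.1.3). Section 5.3 adds that bleeding events "will be assessed by the investigator at every post-surgery visit".
- **Between visits.** At discharge the site stresses to subject and caregiver "the importance of contacting the Investigator immediately if subject experiences signs of clinically over bleeding" (5.3). Section 5.2 also lists discharge instruction cards and an emergency card.
- **Laboratory.** The last scheduled haemoglobin is at discharge.

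The one daily instrument is described in 5.2 as "Daily dosing diaries to be used to record study medication taken". Section 6 says of adverse events generally that "subjects should not be questioned regarding the specific occurrence of one or more AEs".

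The primary endpoint is adjudicated major or CRNM bleeding up to two days after end of treatment. In 5.3 the CRNM criteria include "Single bleeding episode persists for 5 minutes or more" for epistaxis, an unusual bruise, and blood-stained sputum. Protocol 8.3 and SAP 4.1 instead describe CRNM bleeding as needing medical intervention.

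**The concern.** Several of the 5.3 CRNM criteria can be met by a self-limited bleed that leaves no medical record. The adjudication committee can classify only what is reported. If a hip subject has such a bleed on Day 15 and does not think it worth a call, the next scheduled chance to record it is about Day 35. By then the subject must remember it, and Section 6, read literally, discourages the specific question that would prompt the memory.

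Amendment 01 removed the enoxaparin arm, so the result is now an absolute rate, which SAP 1.1 and 3.1 describe as acceptable or not. With no comparator sharing the same under-capture, missed events lower the reported rate directly, in the direction that favours the drug. The recall interval is also much longer for hips than for knees, and both documents plan results by surgery type.

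**Working it through.** **The plan's own precision figure.** Protocol 8.1 and SAP 5 give 500 subjects, a 4.36% rate and a 95% CI of 2.6% to 6.2%, width 3.6%. The Wald interval is p ± 1.96 × √(p(1 − p)/n). With p = 0.0436 and n = 500 it is 2.57% to 6.15%, width 3.58%, half-width about 1.79 points. This agrees apart from rounding of the upper limit. Expected events: 500 × 0.0436 = 21.8.

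**Gap between scheduled contacts** (visit days and windows from 3.1.3):

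| Surgery | Nominal | Shortest | Longest |
|---|---|---|---|
| Hip | 35 − 7 = 28 days | 33 − 9 = 24 | 37 − 5 = 32 |
| Knee | 12 − 7 = 5 days | 10 − 9 = 1 | 14 − 5 = 9 |

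No discharge day is specified. A subject discharged after Day 7 has a later in-hospital assessment and a shorter gap.

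**Share of the hip endpoint window.** With 35 dosing days plus 2, the window is 37 days and 28/37 = 76%. With 33 or 37 dosing days the share is 28/35 = 80% or 28/39 = 72%. This is a share of days, not of events; the documents do not say how bleeds are spread over time.

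**Possible effect on the rate (illustration only).** The documents give none of the inputs below except the 4.36%, which is a pooled planning rate:

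- true rate 4.36% in both surgery types;
- hip share s = 30% to 70% (Protocol 3.1.2 leaves the split open);
- share of hip events falling in the gap f = 20% to 60%;
- share of those missed m = 25% to 50%.

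Observed pooled rate = 4.36% × (1 − s × f × m). Observed hip rate = 4.36% × (1 − f × m).

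- Mildest: s × f × m = 0.3 × 0.2 × 0.25 = 0.015. Pooled 4.29%, hip 4.14%, events lost 21.8 × 0.015 = 0.3.
- Most severe: s × f × m = 0.7 × 0.6 × 0.5 = 0.21. Pooled 3.44% (Wald 95% CI 1.85% to 5.04%), hip 3.05%, events lost 21.8 × 0.21 = 4.6.

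The largest pooled shift is 4.36 − 3.44 = 0.92 points, about half the CI half-width.

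**The two CRNM definitions.** Under 5.3, a five-minute nosebleed or an unusual bruise with no care sought can count, so recall matters. Under 8.3 and SAP 4.1, a bleed needs medical intervention to count, which would usually leave a record. The exposure therefore depends on which text governs.

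**The case against.** The strongest reply is that the plan is not passive. Subject and caregiver are told at discharge to call at once, they carry cards, they are asked at each visit about bleeding since the last one, and the investigator assesses bleeding every time. Major bleeds would mostly bring the patient to care. This stands as far as it goes, but for hips the next visit after Day 7 is still Day 35, and for a trivial-seeming bleed the instruction works only if the subject judges it worth a call.

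Five stronger readings are tempting and are not supported:

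- *That minor bleeds in the primary endpoint are being lost.* Protocol 7.2 lists minor bleeds as a category separate from CRNM bleeds; they are outside the endpoint.
- *That between-visit reports are unprompted.* They are subject-initiated, after an explicit instruction.
- *That a hip-versus-knee comparison is invalidated.* Only descriptive summaries by surgery type are planned, and treatment length (12 versus 35 days) already separates the groups.
- *That the bias has a known size.* Every input to the illustration beyond the planning rate is assumed, and no acceptability threshold is stated that the shift could cross.
- *That the diary is unavailable at phone visits.* Section 3.1.3 says diaries should be collected at Day 7 and Day 12 or 35 and gives no procedure for phone visits. The form itself is not in the documents, so the description in 5.2 is all there is to go on.

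A daily bleeding prompt also sits uneasily with the Section 6 rule, which exists to prevent reporting bias. That objection is fair and the fix has to deal with it. Section 3.1.3 already asks subjects specifically about bleeding, so a prompt limited to the primary endpoint extends what the protocol does.

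**Conclusion.** The point holds as a weakness in ascertainment; it does not make the design invalid. The 28-day against 5-day contact gap and the tablet-only description of the diary are plain in the text. Under the 5.3 definition, CRNM bleeds that need no medical contact therefore depend on subject-initiated calls or Day 35 recall for roughly three quarters of the hip window (72% to 80% across the allowed dosing durations with a 28-day gap).

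The likely direction is downward for the primary rate, more so in hips, and this carries into the summaries by surgery type. The illustrated pooled shift is smaller than the sampling uncertainty, but it runs one way and a larger sample would not remove it. It shrinks if the medical-intervention wording governs. The change is worth making because it is cheap.

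**What to change.** 1. Add one daily line to the existing diary: any bleeding or unusual bruising today, yes or no; if yes, site, duration and care sought. Keep it to bleeding.
2. Have the investigator review the entries at Day 7 and at Day 12 or 35. Send all acute clinically overt bleeds to the adjudication committee, as 5.3 already requires, not only those the site thinks will qualify.
3. State in Section 6 that this primary-endpoint prompt is exempt from the rule against questioning on specific adverse events.
4. Keep the instruction to call immediately.
5. For phone visits, have the entries read out and the diary returned later.
6. Reconcile the CRNM definitions in Protocol 5.3, Protocol 8.3 and SAP 4.1.

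Cost: a reprinted diary, an added eCRF field, and a protocol amendment with IRB/IEC review (Protocol 9.1.1). Sites and the committee will handle more trivial reports, and the reported rate may be higher. No new visit, procedure or staff is needed.
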